15. Ophthalmology evaluations will be conducted at least on Day 1 and at Follow-up by a qualified ophthalmologist and will include visual acuity, pupil exam, confrontation visual field, extraocular motility and alignment, interior slit lamp examination, and dilated fundus examination of the retina. Additional ophthalmology evaluations may be performed at any other time, if indicated, as determined by the investigator.
16. Vital signs will be measured before any blood draws scheduled for the same time point. Vital signs will include blood pressure, respiratory rate, pulse, oxygen saturation, and temperature. On Days 1 and 5, vital signs will be measured at pre-dose and at 6-hour intervals post-dose.
17. At Screening, 12-lead ECGs will be performed in triplicate, with each measurement separated by 2 minutes. The average of the 3 screening ECGs will be used to calculate QTc interval to determine study eligibility. Thereafter, single 12-lead ECGs will be performed for all patients prior to drug administration on Days 1 and 5 of Cycle 1; on Day 1 of each subsequent treatment cycle; and at the Final Study visit.
18. **Cycle 1:** Starting on Day 1 of Cycle 1, digital Holter monitoring will be performed from 45 minutes pre-dose through 24 hours post-dose. ECG extractions of the continuous Holter recordings will be performed at 45, 30, and 15 minutes pre-dose and at specific post-dose time points

coinciding with the serial blood sampling time points for pharmacokinetics. Patients will be instructed to assume a supine position 5-10 minutes prior to each serial blood sampling time point and remain supine throughout the 5-minute ECG extraction period just prior to serial blood sample collection. During the 24-hour Holter monitoring period, a 12-lead ECG tracing may be printed out at any time while the patient is in the clinic at the discretion of the investigator. If for any reason Holter monitoring is not performed in conjunction with the PK sampling on Day 1 or the tracings are of poor quality, Holter monitoring may be performed in conjunction with the PK sampling on Day 5.

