19. **Cycle 1:** Serial, 3-mL blood samples will be taken for determination of plasma CPX-POM and metabolites concentrations during Cycle 1 at 0.25, 0.5, 1.0, 1.5, 2.0, 3.0, 4.0, 5.0, 6.0, 8.0, 10.0, 12.0, and 24.0 hours following completion of the 10-minute IV infusion on Day 1 and on Day 5. Each PK sample should be collected as close as possible to the planned time. The 12.0 hour collection can have a +/- 1-hour window (collect within 11 to 13 hours) and the exact time must be recorded. The actual date and time of each blood sample collection will be accurately recorded.
20. **Cycle 1:** Complete 24-hour urine samples for determination of CPX-POM and metabolites concentrations, and measurement of urine volume will be obtained from each patient in urine collection and storage containers during Cycle 1. A sample will be taken at pre-dose on Day 1, and complete urine samples will be collected at 0-12 and 12-24 hour collection intervals post-dose on Days 1 and 5. The 12 hour collection can have a +/- 1-hour window (collect within 11 to 13 hours) and the exact time must be recorded.
21. **Cycle 1:** Urine β -glucuronidase activity will be determined in the complete 24-hour urine samples collected on Day 1 and Day 5 of Cycle 1.
22. 7-mL blood samples will be obtained in EDTA-containing blood collection tubes at pre-dose on Day 1 and Day 5 of each treatment cycle, and on Day 22 of the last treatment cycle. Plasma and buffy coat (PBMCs) will be isolated, transferred to storage tubes, and stored frozen.
23. BSA will be calculated by the site personnel using the Dubois method of calculation using screening height and baseline weight measurements. BSA is to be recalculated before study drug administration on Day 1 of every other treatment cycle, starting with Cycle 3 and the patient's study drug dose adjusted accordingly.
24. CPX-POM infusions will be administered once every 24 hours as 10-minute IV infusions on Days 1-5 of each 21-day treatment cycle. After completion of Cycle 1 for the first 4 to 6 patients, the SRC will review safety, PK, and PD data to determine if any changes to the dosing schedule are indicated (e.g., adding an additional 5 days of dosing to each treatment cycle).

GLOSSARY OF ABBREVIATIONS AND DEFINITION OF TERMS

| | |
|----------------------|---|
| AE | adverse event |
| ALT | alanine aminotransferase |
| ANC | absolute neutrophil count |
| aPTT | activated partial thromboplastin time |
| AST | aspartate aminotransferase |

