Scientists at the University of Kansas synthesized the phosphoryloxymethyl ester of CPX, CPX-POM to enable parenteral administration of CPX. In contrast to CPX and CPX-O, CPX-POM has high water solubility and is readily formulated for parenteral administration.

Pharmacokinetic (PK) studies in laboratory animals showed that CPX-POM is rapidly and completely metabolized to its active metabolite, CPX, which then disappears from plasma following systemic administration of CPX-POM. Following systemic administration of CPX-POM, the dose is eliminated from the body via renal clearance of CPX and the inactive glucuronide metabolite of CPX (CPX-G).

In rats, intravenous (IV) CPX-POM administered for 28 consecutive days did not cause mortality or changes in body weight, food consumption, ophthalmology, hematology, coagulation, clinical chemistry, urinalysis, or organ weights. There were no test item-related findings grossly or microscopically at the highest dose level tested (50 mg/kg/day). Test item-related transient clinical signs, including slight to moderate decreased activity, increased respiration, eating-like behavior, and slight to moderate incoordination were noted immediately after dosing at 50 mg/kg/day. The no observed adverse effect level (NOAEL) in rats was 25 mg/kg/day in males and 50 mg/kg/day in females.

In dogs, CPX-POM administered for 28 consecutive days did not cause mortality or changes in body weight, food consumption, electrocardiogram (ECG) parameters, hematology, coagulation, clinical chemistry, urinalysis, or organ weights. There were no test item-related findings grossly or microscopically at dose levels up to 30 mg/kg/day. Test item-related transient clinical signs such as salivation, fecal changes, aggression, shaking, and tremors were noted after dosing at the highest dose level tested on the study (30 mg/kg/day). Convulsion was apparent in one dog on a single occasion. Test-item related ophthalmic changes were noted in 3/10 dogs treated with 30 mg/kg/day. Thus, the NOAEL in dogs was determined to be 10 mg/kg/day and the highest non-serious toxic dose (HNSTD) in the dog was determined to be 30 mg/kg.

The starting dose of CPX-POM in patients was selected based on the results of the IV CPX-POM 28-day Good Laboratory Practices (GLP) toxicology studies conducted in the rat and dog and consistent with FDA guidance ([FDA, 2010](#)) (see Section 4.4).

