4.4. Dose Selection

Food and Drug Administration guidelines (FDA, 2010) were employed to determine the starting dose for this study, 30 mg/m². As described in this guidance, a common approach for determining a starting dose for small molecule drugs is to use one-tenth the severely toxic dose in 10% of the animals (STD10) in rodents OR one-sixth the highest non-severely toxic dose (HNSTD) in non-rodents. In GLP toxicology studies in rats, the CPX-POM STD10 was not reached, so the highest dose tested (50 mg/kg) was used to determine a safe human starting dose of 30 mg/m² (one-tenth the STD10 based on mg/m²). In GLP toxicology studies in dogs, the CPX-POM HNSTD was 10 mg/kg based on tremors and convulsion observed at 30 mg/kg. One-sixth of the HNSTD observed in dogs, converted to mg/m², also supports a starting dose of 30 mg/m² in patients.

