6.1.4. Dosage and Administration

CPX-POM will be administered as an IV infusion once daily on Days 1-5 of each 21-day treatment cycle. CPX-POM will be added to a 100 mL piggyback bag of 0.9% sodium chloride solution and infused over a 10-minute period. The initial dose for the first patient enrolled (i.e., Cohort 1) will be 30 mg/m².

At baseline, the body surface area (BSA) will be calculated by the Dubois method using Screening height and baseline weight measurements. The baseline BSA is to be used to determine the patient's study drug dose. Thereafter, BSA is to be recalculated on Day 1 of every other treatment cycle, starting with Cycle 3, and the patient's study drug dose adjusted accordingly.

$$\text{Dubois Formula: } \text{BSA} = 0.007184 \times W^{0.425} \times H^{0.725}$$

The dose escalation procedure is described in Section 4, and further details and example doses are shown in Section 4.2.

After completion of Cycle 1 for the first 4 to 6 patients, the SRC will review safety, PK, and PD data to determine if any changes to the dosing schedule are indicated (e.g., adding an additional 5 days of dosing to each treatment cycle).

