Replicate of Listing 16.2.8-1

PROGRAMMING NOTES:

- Listing to be sorted by increasing order.
- Only Day 1 of each cycle.

Listing 16.2.8-4 - Patients Laboratory Profile: Urinalysis
(All Patients)

Replicate of Listing 16.2.8-1

PROGRAMMING NOTES:

- Listing to be sorted by increasing order.
- Replace 'Day 4' by 'Day 5' for each cycle.

Sponsor: CicloMed
Protocol: CPX-POM-001
Statistical Analysis Plan
(TFL shells):
Version 1.0 / 02FEB2018

Protocol: CPX-POM-001

--- DELIVERY TYPE ---

Page 1 of X

Listing 16.2.8-5 - Vital Signs
 (All Patients)

CPX-POM Dose Group: 30 mg/m²

Center/ Patient	Visit	Assessment		Study Day	Parameter (unit)	Position	Result	Change from Baseline
		Date	Time					
XXXX	BAS	DDMMYYYY	HH:MM	XXX	Pulse Rate (bpm)	Supine	XXX +	
					Respiratory Rate (bpm)	Supine	XXX	
					Systolic BP (mmHg)	Supine	XXX	
					Diastolic BP (mmHg)	Supine	XXX	
					Oxygen Saturation (mmHg)		XXX	
					Body Weight (kg)		XXX.X	
					Temperature (C)		XX.X	
	C1 TRT D2	DDMMYYYY	HH:MM	XXX	Pulse Rate (bpm)	Supine	XXX +	XX
					Respiratory Rate (bpm)	Supine	XXX	XX
					Systolic BP (mmHg)	Supine	XXX	XX
					Diastolic BP (mmHg)	Supine	XXX	XX
					Oxygen Saturation (mmHg)		XXX	XX
					Body Weight (kg)		XXX.X	X.X
					Temperature (C)		XX.X	X.X

<repeat for Day 3, Day 4, Day 5, Day 6 and Day 10 visits of Cycle 1>
 <for Cycle 2 to last-1 cycle, repeat from Day 1 to Day 6 visits if relevant>
 <for the last cycle, repeat also for Day 22 visit and Day 28 follow-up visit>

Study Day was from the date of first dose of CPX-POM administration. Dates are displayed as DDMMYYYY. Baseline was the last non-missing assessment prior or on the first dose.

+ Results of clinical importance (see SAP). BP = Blood Pressure; bpm = beats per minute; ND = Not Done.

Program: (Program name.sas) (run on: DDMMYYYY HH:MM)

Filename: (Specify file name.rtf)

PROGRAMMING NOTES:

- Repeat for all doses groups

Sponsor: CicloMed
Protocol: CPX-POM-001
Statistical Analysis Plan
(TFL shells):
Version 1.0 / 02FEB2018

Protocol: CPX-POM-001

--- DELIVERY TYPE ----

Page 1 of X

Listing 16.2.8-6 - ECG Results and Interpretation
 (All Patients)

CPX-POM Dose Group: 30 mg/m²

Center/ Patient	Visit	Assessment Date (Day)	Parameter (unit)	Clinician Interpretation	Result	Change from baseline
XXXX	BAS	DDMMYYYY (XXX)	Heart Rate (bpm)	Normal	XXX	
			PR interval (msec)	Normal		
			QRS duration (msec)	Normal		
			QT interval (msec)	Normal		
			QTcB interval (msec)	Normal		
			QTcF interval (msec)	Normal		

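### No blood pressure, respiratory rate or oxygen saturation is scheduled in the first 6 hours after the infusion, and the SAP shells draw no explicit Cycle 1 Day 1 post-dose vital-sign row

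*Protocol*

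**What the plan says.** **Protocol.** Section 1.3, Table 1, footnote 16 sets the timing: "On Days 1 and 5, vital signs will be measured at pre-dose and at 6-hour intervals post-dose". Section 8.2.3.4 refers back to Table 1 for the times and adds only an order of procedures at shared time points. For Days 2 to 4 no time relative to the infusion is given. Under Section 6.1.4 the drug is "infused over a 10-minute period".

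Section 2 gives the animal findings. In rats, "increased respiration, eating-like behavior, and slight to moderate incoordination were noted immediately after dosing at 50 mg/kg/day". In dogs at 30 mg/kg/day there were tremors and shaking, and "Convulsion was apparent in one dog on a single occasion".

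On Cycle 1 Day 1, footnote 18 states that "digital Holter monitoring will be performed from 45 minutes pre-dose through 24 hours post-dose", with ECGs extracted at the pharmacokinetic times. Footnote 19 sets those times "at 0.25, 0.5, 1.0, 1.5, 2.0, 3.0, 4.0, 5.0, 6.0, 8.0, 10.0, 12.0, and 24.0 hours following completion of the 10-minute IV infusion".

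**SAP (table and listing shells).**
- Table 14.3-3.2 goes from baseline to Cycle 1 Day 2.
- Table 14.3-3.1 replicates the hematology summary, Table 14.3-2.1.1. A programming note beneath it repeats the 6-hourly timing for Days 1 and 5.
- Listing 16.2.8-5 shows a baseline visit and Cycle 1 Day 2, then the instruction "repeat for Day 3, Day 4, Day 5, Day 6 and Day 10 visits of Cycle 1".
- In both tables, baseline is the last result obtained before the first treatment day or on that day.

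**The concern.** The drug goes in over 10 minutes, and the protocol's own toxicology shows at least one sign, faster respiration, that appears at once and passes. A reading at 6 hours may come after such an effect has gone. A short, symptomless change in pressure, respiration or saturation is found only by measuring it.

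This bears on the primary objective. Doubling in single patients continues until a toxicity of Grade 2 or higher is seen, and hypertension enters the DLT definition through a stated exception. The Safety Review Committee would decide on escalation without these measures from the period closest to dosing.

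The reporting side adds to this. If the 6- and 12-hour values after the first human dose have no row, or are used as baseline, the tables cannot show a change on that day. Later changes could then be measured from a value that already contains a drug effect.

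**Working it through.** No stated figure in the plan needs reproducing. The check is counting, one conversion and a comparison of row structures.

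**1. Length of the gap.** Inputs: first scheduled post-dose vital signs at 6 h (footnote 16); infusion of 10 min (Section 6.1.4).
- 6 h × 60 = 360 min; 360 / 10 = 36 infusion lengths.
- Footnote 19 times before 6 h: 0.25, 0.5, 1, 1.5, 2, 3, 4 and 5 h, so 8 of 13.
- Patients stay at least 12 h on Days 1 and 5 of Cycle 1 (footnote 1). The 6-hourly grid gives 2 post-dose sets in that time, at 6 h and 12 h.
- Scheduled sets of blood pressure, respiratory rate and saturation after dosing and before 6 h: 0.

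**2. Relevance of the rat dose.** Section 4.4 describes 30 mg/m² as "one-tenth the STD10 based on mg/m²", with 50 mg/kg, the highest rat dose tested, standing in for the STD10 because that was not reached.
- Implied rat dose: 30 × 10 = 300 mg/m².
- Starting dose: 30 / 300 = 0.10 of it.
- Example doses in Table 4: 240 / 300 = 0.80; 350 / 300 = 1.17; 475 / 300 = 1.58; 600 / 300 = 2.00.

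The rat signs therefore say little about the first cohort, but they lie within the range that the protocol's own examples cover.

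**3. SAP rows for Cycle 1 Day 1 after dosing.**
- Table 14.3-3.2: none. The first row after baseline is Day 2. Day 5 falls under the instruction to repeat for later Cycle 1 visits, but without time points. The shell is drawn for pulse, systolic and diastolic pressure only, so respiratory rate and saturation depend on Table 14.3-3.1.
- Table 14.3-3.1: none. The replicated shell has baseline, Cycle 1 Day 4 and Cycle 1 Day 10. The note beneath names post-dose times on Days 1 and 5, for which the shell has no rows, so the note and the rows conflict.
- Listing 16.2.8-5: no labelled row. Day 1 values could sit under the baseline visit by clock time, because the listing has a time column.

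**4. Baseline.** Read literally, the table definition takes the last value up to and including the first treatment day. With readings pre-dose and at 6 h and 12 h on Day 1, the last one is at 12 h, after dosing. The listing words its baseline slightly differently, by reference to the first dose, so the two should also be aligned.

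**The case against.** A reader might infer that acute effects are neither measured nor reported. The documents do not support that.
- Holter recording runs through the infusion and the first 6 hours of Cycle 1 Day 1, with 8 extraction times before 6 h.
- Symptoms and toxicities are assessed, and adverse events collected, at every treatment visit, including Day 1 with its stay of at least 12 hours.
- Adverse events have tables and a listing. Listing 16.1.7-2 gives the time of and reason for each interrupted infusion.

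Most of the animal findings, such as incoordination, tremor and convulsion, are signs that an observer sees and a cuff or oximeter does not. Only increased respiration corresponds to a vital sign. Section 2 reports no blood-pressure or saturation finding in either species, and dog ECG parameters were unchanged. A missed hemodynamic effect is therefore not something the animal data predict. Escalation turns on graded toxicity, DLTs and committee review, not on vital-sign tables.

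On the SAP, the supplied document consists of shells that refer to a main text not available here. The note under Table 14.3-3.1 shows that the post-dose times were known. The treatment listing places the first infusion under the baseline visit, so Listing 16.2.8-5 may be meant to hold Day 1 values there.

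All of this narrows the point without removing it. Holter recording gives rhythm and QTc, not pressure, respiration or saturation. Section 9.5.5 promises a Holter summary, but the shells contain none. The adverse-event listing has dates without clock times, so it cannot tie an event to the infusion. The order of procedures in Section 8.2.3.4 schedules no reading after the infusion on Days 2 to 4.

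**Conclusion.** The point holds in a limited form. Blood pressure, respiratory rate and oxygen saturation have no scheduled reading between pre-dose and 6 hours on Days 1 and 5. That is 360 minutes after a 10-minute infusion, with 8 existing draws inside the gap. The post-dose values that are collected on Cycle 1 Day 1 have no row in Table 14.3-3.2 or in the shell behind Table 14.3-3.1, and no explicit row in Listing 16.2.8-5. The baseline definition permits a post-dose value.

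How much of an effect would be missed cannot be sized, because the documents give no duration for the rat signs beyond calling them transient. The 300 mg/m² figure rests on the protocol's own one-tenth rule. The SAP finding rests on the shells alone; the main SAP text may settle the baseline and the time points, and should be checked first. The point is worth acting on because it affects what the Safety Review Committee sees and what is reported. It does not show that acute toxicity would go undetected.

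**What to change.** **SAP.**
- Add Cycle 1 Day 1 and Day 5 post-dose rows by time point, and the worst post-dose value per patient, to Tables 14.3-3.1 and 14.3-3.2.
- Label the same time points in Listing 16.2.8-5.
- Define the vital-sign baseline as the last value before the first infusion, in tables and listing alike.

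**Protocol.** Reconcile footnote 16 with the findings in Section 2 by adding vital-sign readings soon after infusion at some of the pharmacokinetic draws already scheduled before 6 h. The sponsor should choose the times; nothing in the documents singles out particular ones. Record the time of vital signs relative to the infusion on Days 2 to 4.

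**Cost.** A few extra non-invasive readings during a stay that already lasts at least 12 hours, one amended footnote and some shell rows. Where Day 5 pharmacokinetic sampling moves to Cycle 2, as footnote 1 allows, the added readings move with it and the Day 5 rows need to allow for that.

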| CPX-POM infusions ²⁴ | | X | X | X | X | X | | | | |

Abbreviations: ALP = alkaline phosphatase; ALT = alanine aminotransferase; aPTT = activated partial thromboplastin time; AST = aspartate aminotransferase; BSA = body surface area; BUN = blood urea nitrogen; CPX-POM = ciclopirox phosphoryloxymethyl ester; CT = computed tomography; D = day; ECG = electrocardiogram; ECOG = Eastern Cooperative Oncology Group; EDTA = ethylenediamine tetraacetic acid; eGFR = estimated glomerular filtration rate; GGT = gamma glutamyl transferase; HIV = human immunodeficiency virus; IV = intravenous; MUGA = multi-gated acquisition; MRI = magnetic resonance imaging; PBMC = peripheral blood mononuclear cell; PD = pharmacodynamic; PK = pharmacokinetic; PT = prothrombin time; RBC = red blood cell; T3 = triiodothyronine; T4 = thyroxine; TSH = thyroid stimulating hormone; V = visit; WBC = white blood cell.

1. On Days 1 and 5 of Cycle 1, patients will be required to stay at the clinical research unit for at least 12 hours for PK sampling and other assessments. If patients are unable or unwilling to attend the required 12 hours of clinic visitation required for steady-state PK sampling on Day 5 of Cycle 1, the steady-state PK sampling may be postponed to Day 5 of Cycle 2. To shorten the duration of the Cycle 1, Day 1 visit, if needed, the safety laboratory blood samples required for this visit may be drawn up to 3 days before Day 1.
2. The Day 10 (Visit 8) study visit will only be required during Cycle 1.
3. After cycle 1; visit windows can be considered on a case by case basis due to events such as holidays; Cycle 1 needs to occur without visit windows. D6 can occur +2 calendar days for cycles after Cycle 1 is completed.
4. If final treatment cycle, patient returns for assessments on Day 22. If additional cycles are planned, patient skips this visit and restarts schedule at Day 1 (except for PK). Patients may continue to receive cycles of CPX-POM until progression of disease, intolerable toxicity occurs, or another withdrawal criterion applies.

5. The Follow-up visit will occur 28±5 days after the last dose of CPX-POM administered during the last treatment cycle. Or, in the event that a patient discontinues from the study prematurely, the site will make every effort to perform the assessments listed for this study visit.
6. Hepatitis screening will include tests for Hepatitis A, Hepatitis B, and Hepatitis C.

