8.2.3.5. Electrocardiograms and Holter Monitoring

At Screening, 12-lead ECGs will be performed in triplicate, with each measurement separated by 2 minutes. The average of the 3 screening ECGs will be used to calculate QTc

and QTcF (Fridericia's formula):
$$QTc = \frac{QT}{\sqrt[3]{RR}}$$

to determine study eligibility. Thereafter, single 12-lead ECGs will be performed at the dates and times indicated in the Schedule of Assessments (Table 1).

On Day 1 of Cycle 1, digital Holter monitoring will be performed from 45 minutes pre-dose through 24 hours post-dose in order to examine any potential QTc changes and relate those, if present, to simultaneously obtained blood samples for plasma drug and/or metabolite concentration determination. ECG extractions of the continuous Holter recordings will be performed at 45, 30, and 15 minutes pre-dose and at specific post-dose time points coinciding with the serial blood sampling time points for PK. Patients will be instructed to assume a supine position 5 to 10 minutes prior to each serial blood sampling time point and remain supine throughout the 5-minute ECG extraction period just prior to serial blood sample collection. During the 24-hour Holter monitoring period, a 12-lead ECG tracing may be printed out at any time while the patient is in the clinic at the discretion of the investigator.

If for any reason Holter monitoring is not performed in conjunction with the PK sampling on Day 1 or the tracings are of poor quality, Holter monitoring may be performed in conjunction with the PK sampling on Day 5.

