8.3. Pharmacokinetic Assessments

Serial, 3-mL blood (plasma) samples will be taken for PK analysis of CPX-POM and metabolites at the times and days shown in the Schedule of Assessments (Table 1). Each PK sample should be collected as close as possible to the planned time. The actual date and time of each blood sample collection will be recorded. PK samples may not be obtained from the same site where CPX-POM is infused.

Urine samples for PK analysis of CPX-POM and metabolites and measurement of urine volume will be obtained from each patient in urine collection and storage containers. Samples will be collected during Cycle 1 only at the times and days shown in the Study Procedures Manual and the Schedule of Assessments (Table 1). Urine β -glucuronidase activity will be determined in the urine samples collected for PK analysis.

The actual date and time of each sample collection, and the date and time of the previous dose of CPX-POM will be recorded. Processing, storage, and shipping procedures are provided in the Study Procedures Manual.

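### The Day 1 24-hour plasma PK sample is timed from the end of the infusion, and the protocol does not say that it precedes the Day 2 infusion

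*Protocol*

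**What the plan says.** Protocol section 1.3, Table 1, footnote 19 lists 13 plasma sampling times from 0.25 h onward, ending at "12.0, and 24.0 hours following completion of the 10-minute IV infusion on Day 1 and on Day 5". Footnote 24 of the same table gives the dosing: "CPX-POM infusions will be administered once every 24 hours as 10-minute IV infusions on Days 1-5 of each 21-day treatment cycle". Table 1 marks both PK blood samples and an infusion on Day 2, without an order.

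On tolerance, section 8.3 says "Each PK sample should be collected as close as possible to the planned time", and footnote 19 says the same. The only plasma window is for another sample: "The 12.0 hour collection can have a +/- 1-hour window (collect within 11 to 13 hours) and the exact time must be recorded". Footnote 3 adds that "Cycle 1 needs to occur without visit windows".

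Elsewhere the protocol does state the order of sampling and dosing. Footnote 22 puts the biomarker samples "at pre-dose on Day 1 and Day 5 of each treatment cycle".

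The Holter recording (footnote 18) and the urine intervals (footnote 20) are counted post-dose rather than from completion of the infusion. Yet the Holter extractions are taken "at specific post-dose time points coinciding with the serial blood sampling time points for PK", in the 5 minutes before each draw.

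Section 9.6.1 derives AUC[0-t], AUC[t-∞], AUCinf and systemic clearance for the single Day 1 dose. It also derives an AUC accumulation ratio that has the single-dose AUC as its denominator.

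**The concern.** The sampling clock starts when the infusion ends, and the dosing clock presumably starts when it begins. The two differ by the 10-minute infusion time, which is enough to put a nominal end-of-interval trough at the end of the next infusion. A site that draws first records a Day 1 trough. A site that keeps a strict 24-hour start-to-start interval and the nominal sampling time records a level that includes the second dose. Both could regard themselves as compliant.

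The 24-hour point is the only Day 1 sample after 12 h, so it determines the last trapezoid of AUC[0-t] and normally enters the terminal slope. A missed trough cannot be collected again. In single-patient cohorts, one affected profile is all the Day 1 PK at that dose level. The Safety Review Committee looks at PK, with safety and PD, after Cycle 1 of the first 4 to 6 patients.

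**Working it through.** **Clock arithmetic (footnotes 19 and 24).** Take the start of the Day 1 infusion as time zero.

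- Day 1 infusion: 0 h 00 min to 0 h 10 min.
- Last Day 1 sample: 0 h 10 min + 24 h 00 min = 24 h 10 min.
- Day 2 infusion, 24 h start-to-start: 24 h 00 min to 24 h 10 min. The sample falls at its end, a gap of 0 minutes.
- Day 2 infusion, 24 h end-to-start: it begins at 24 h 10 min. The sample falls at its start.
- Day 5: under Days 1–5 dosing no infusion follows on Day 6, so the Day 5 sample is clear.

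**Consequence if the sample is taken at the end of the Day 2 infusion and kept.** The documents give no human half-life, so a range is assumed. The model has one compartment and linear kinetics, with the end-of-infusion concentration set to 1 and time t counted from completion. Then C(t) = exp(−kt), with k = ln 2 / half-life. The literal 24 h value is 1 + C(24). AUC uses the linear-up/log-down rule.

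Worked case, half-life 8 h (k = 0.08664 per h):

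- C(0.25) = 0.9786, C(12) = 0.3536, C(24) = 0.125.
- Literal 24 h value: 1.125, which is 1.125 / 0.125 = 9 times the true residual and 1.125 / 0.3536 = 3.2 times the 12 h value.
- Infusion start to first sample: (0.1667 + 0.25) × 0.9786 / 2 = 0.204.
- 0.25 to 12 h: (0.9786 − 0.3536) / 0.08664 = 7.214.
- Last interval, sample 5 min before the Day 2 infusion (t = 23.75 h, C = 0.1277): (0.3536 − 0.1277) / 0.08664 = 2.61.
- Last interval, literal sample (rising, so linear): 12 × (0.3536 + 1.125) / 2 = 8.87.
- AUC[0-t] ratio: (0.204 + 7.214 + 8.87) / (0.204 + 7.214 + 2.61) = 16.29 / 10.03 = 1.62.
- Log-linear slope through the 10, 12 and 24 h points: λ = −0.079 per h. The fitted line rises, so it gives no half-life and no extrapolated area.

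The second model is a metabolite formed with an assumed 5-minute conversion half-life. It is relevant because protocol section 2 reports rapid and complete conversion of the prodrug in animals. Each ratio is the literal draw over the draw 5 minutes before the Day 2 infusion.

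| Assumed half-life | AUC[0-t] ratio, one-compartment | AUC[0-t] ratio, metabolite | Literal 24 h value ÷ 12 h value, one-compartment |
|---|---|---|---|
| 2 h | 3.13 | 1.96 | 64 |
| 4 h | 2.10 | 1.52 | 8.1 |
| 6 h | 1.78 | 1.37 | 4.3 |
| 8 h | 1.62 | 1.30 | 3.2 |
| 12 h | 1.48 | 1.23 | 2.5 |

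The three-point slope has the wrong sign in both models at every half-life tried, from 1 to 12 h.

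**With the sample before the Day 2 infusion.** The same slope returns the assumed half-life in every case, and AUC[0-t] is 0.74 to 0.99 of the true AUCinf.

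**With the sample excluded instead.** AUCinf stays within about 9% of the truth, but the extrapolated share rises to about 13% at a 4 h half-life, 36% at 8 h and 50% at 12 h.

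**The case against.** The strongest reply is that the collision is one reading only. The synopsis and section 6.1.4 call for daily dosing, and nothing fixes the infusion to the minute. A site can draw at 24 h 10 min and then dose, and it satisfies both footnotes. On the end-to-start reading contamination would be small. Section 9.6.1 ties the Day 1 AUC and clearance parameters to a single dose, which shows the intent. All of this stands. A reader might infer that exact compliance must yield a contaminated sample; the documents support only that the order is undefined and that one natural reading contaminates it.

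A reader might also infer that the last Holter extraction is recorded during the Day 2 infusion. Footnote 18 ends the recording at 24 hours post-dose. Counted from the start of dosing, that is the moment the Day 2 infusion begins, so the recording would stop before any such extraction. What stands is that the Holter limit and the PK time points do not share an origin. The same start-based count ends the 12–24 h urine interval as the Day 2 infusion starts, so no separate urine defect is claimed.

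The error is also detectable. Section 8.3 records the actual sample time and the previous dose time, and a 24 h value well above the 12 h value would stand out. This limits the harm but does not restore the lost trough. Nor can the lack of an exclusion rule be asserted for the whole plan. The SAP supplied consists of table and listing shells, one of which refers to SAP text that was not supplied, and the Study Procedures Manual was not available either.

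**Conclusion.** The point holds as a timing ambiguity that should be fixed. Footnotes 19 and 24 place the last Day 1 plasma sample at the end or at the start of the Day 2 infusion, depending on how the 24 hours are counted. Nothing in the supplied text puts the draw first.

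The bias is conditional: the sample must be drawn at the literal start-to-start time and kept in the analysis. Day 1 AUC[0-t] is then inflated about 1.5 to 3.1-fold (one-compartment, half-life 12 to 2 h) or about 1.3 to 2.0-fold (rapidly formed metabolite, 8 to 2 h). A slope through the point rises, which undermines Day 1 AUCinf, clearance and the AUC accumulation ratio. The sizes rest on assumed half-lives and models; the direction does not change over 1 to 12 h.

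Two wider inferences are not supported. Half-life is not lost to the study: section 9.6.1 does not tie it to Day 1, and the Day 5 profile is clean under the present schedule. A wrong Day 1 Cmax is not established either. The literal 24 h value exceeds the first post-infusion sample in the one-compartment model, but it is only 0.51 to 0.73 of the Day 1 peak in the metabolite model.

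PK is a secondary objective and the Table 2 escalation rules rest on toxicity and DLT counts, so this does not threaten the primary objective.

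**What to change.** - In footnote 19, state that the Day 1 24-hour plasma sample is drawn before the start of the Day 2 infusion, with the actual time recorded.
- Put footnotes 18, 19, 20 and 24 on one stated time origin, so that the last Holter extraction precedes that draw.
- In the PK analysis text, exclude from the Day 1 parameters any sample whose recorded time is after the start of the Day 2 infusion. If the full SAP text or the Study Procedures Manual already says this, cross-refer to it.
- If the Safety Review Committee adds dosing days that follow directly on Day 5, check the Day 5 24-hour sample for the same overlap.

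The cost is a sentence or two in the footnotes and one analysis rule. No visit, sample or dose is added. The nominal time of one sample moves by about 10 minutes, which is immaterial when actual times are used.
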